### **11.3.9 Serious Adverse Event Reporting**

#### **11.3.9.1 Governing Regulatory Requirements**

Compliance with this request for prompt reporting is essential in that the sponsor is responsible for informing the US FDA as well as all other participating investigators of the event.

Under FDA ruling (Title 21 CFR Part 312.32) and the Guidance for Industry and Investigators Safety Reporting Requirements for INDs and BA/BE Studies, the sponsor is required to submit written documentation, in the form of an IND safety report, detailing:

- Any event associated with the use of the drug, that is both serious and unexpected, or
- Any findings from clinical, epidemiological, or pooled analysis of multiple studies or any findings from animal or in vitro testing that suggest a significant risk in humans exposed to the drug.

Written submission must be made by the sponsor to the FDA and the IRBs as soon as possible and in no event later than 15 calendar days after the sponsor's initial receipt of notification of the event. Any unexpected death or life-threatening suspected adverse reaction must be reported to FDA no later than 7 calendar days after the sponsor's initial receipt of the information. The sponsor shall also inform all investigators.

#### **11.3.9.2 Time-Frame for Reporting**

Any death, pregnancy, SAE, or unexpected (and severe) AE experienced by a subject after ICF or within 30 days of receiving study drug, regardless of relationship to study drug, or any death that occurs more than 30 days after receiving study drug, and is believed to be study drug-related, must be promptly reported (within 24 hours of the investigator becoming aware of the event) by e-mail to the sponsor (or sponsor's designee).

Contact information for **SAE/SUSAR** reporting:

INC Drug Safety  
[contact]  
Email: [[contact]](mailto:[contact])

Additionally, the investigator will be able to contact the **medical monitor** at all times:

[name], MD  
Kadmon Corporation  
[name]  
[name]  
Telephone: [contact]  
E-mail: [contact]

### **11.3.9.3 Information to be Provided by the Investigator**

SAEs for all enrolled subjects must be recorded on both the SAE form and the AE eCRF page. This requirement includes all SAEs that occur after the subject signs the ICF and through 30 days after last dose of study treatment, and in addition, any SAEs that are assessed as possibly related to study treatment by the investigator, even if the SAE occurs more than 30 days after the last dose of study treatment must be reported to the Kadmon Pharmacovigilance Department.

The minimum information required for SAE reporting includes identity of investigator, site number, subject number, an event description, SAE term(s), onset date, the reason why the event is considered to be serious (i.e., the seriousness criteria) and the investigator's assessment of the relationship of the event to study treatment. Additional SAE information including medications or other therapeutic measures used to treat the event, action taken with the study treatment due to the event, and the outcome/resolution of the event will be recorded on the SAE form. Forms for reporting SAEs will be provided to the study sites.

In all cases, the investigator should continue to monitor the clinical situation and report all material facts relating to the progression or outcome of the SAE. Furthermore, the investigator may be required to provide supplementary information as requested by the Kadmon Drug Safety personnel or designee.

When reporting an SAE, the following additional points should be noted:

- When the diagnosis of an SAE is known or suspected, the investigator should report the diagnosis or syndrome as the primary SAE term, rather than as signs or symptoms. Signs and symptoms may then be described in the event description. For

example, dyspnea should not be used as an SAE term if the diagnosis which caused the dyspnea is known to be malignant pleural effusion.

- Death should not be reported as an SAE, but as an outcome of a specific SAE, unless the event preceding the death is unknown. In the exceptional case where the events leading to death are unknown, then death may be used as an event term. If an autopsy was performed, the autopsy report should be provided.
- While most hospitalizations necessitate reporting of an SAE, some hospitalizations do not require SAE reporting, as follows:
  - Elective or previously scheduled surgery (e.g., a previously scheduled ventral hernia repair)
  - Procedures for pre-existing conditions that have not worsened after initiation of treatment
  - Pre-specified study hospitalizations for observation
  - Events that result in hospital stays of less than 24 hours and that do not require admission (e.g., an emergency room visit for hematuria that results in a diagnosis of cystitis and discharge to home on oral antibiotics)
- SAEs must, however, be reported for any surgical or procedural complication resulting in prolongation of the hospitalization.

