### 11.3.1 Serious Adverse Events

(Notify sponsor or designee within 24 hours; document on eCRF)

The SAE definition and reporting requirements are in accordance with Title 21 Part Code of Federal Regulations (CFR) 312.32 and the Guidance for Industry and Investigators Safety Reporting Requirements for Investigational New Drug (IND) applications and bioavailability/bioequivalence (BA/BE) studies.

SAE: An adverse event is considered “serious” if, in the view of either the investigator or sponsor, it results in any of the following outcomes:

- **Death:** This includes any death that occurs while the subject is “on study” as well as any death that occurs within 30 days after study drug administration.

**Note:** Death is an outcome of an AE, and not an AE in itself. The event(s) that caused death (e.g., illness, accident) is the SAE. Death due to any other cause(s) must also be reported as an outcome of the reportable SAE.

- **Life-threatening AE:** An AE or suspected adverse reaction is considered “life-threatening” if, in the view of either the investigator or sponsor, its occurrence places the subject at immediate risk of death. It does not include an AE or suspected adverse reaction that, had it occurred in a more severe form, might have caused death.

- **Inpatient hospitalization or prolongation of existing hospitalization:**

In the absence of an AE, the investigator should not report hospitalization or prolongation of hospitalization. This is the case in the following situations:

- Hospitalization or prolongation of hospitalization is needed for a procedure required by the protocol
- Hospitalization or prolongation of hospitalization is part of routine procedure followed by study center
- Hospitalization for survey visits or annual physicals

In addition, a hospitalization planned before the start of the study for a pre-existing condition which has not worsened does not count as an SAE.

- **Persistent or significant incapacity or substantial disruption of the ability to conduct normal life functions**
- **Congenital anomaly/birth defect**
- **Important medical event:** An event that may not result in death, be life threatening, or require hospitalization may be considered serious when, based upon appropriate medical judgment, it may jeopardize the subject and may require medical or surgical intervention to prevent 1 of the outcomes listed in this definition.

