### **11.3.8 Hospitalization**

In the absence of an AE, the investigator should not report hospitalization or prolongation of hospitalization. This is the case in the following situations:

- Hospitalization or prolongation of hospitalization is needed for a procedure required by the protocol.
- Hospitalization or prolongation of hospitalization is part of routine procedure followed by study center.
- Hospitalization for survey visits or annual physicals.

In addition, a hospitalization planned before the start of the study for a pre-existing condition that has not worsened does not count as an SAE.

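### Protocol 11.3.9.3 exempts elective or previously scheduled surgery from SAE reporting without the conditions in 11.3.1 and 11.3.8, so such an operation for a new or worsened condition may or may not count as an SAE

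*Protocol*

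**What the plan says.** Three places in the protocol say when a hospital stay need not be treated as an SAE.

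- **Section 11.3.1** (the SAE definition): "a hospitalization planned before the start of the study for a pre-existing condition which has not worsened does not count as an SAE".
- **Section 11.3.8** (Hospitalization) repeats the rule: "a hospitalization planned before the start of the study for a pre-existing condition that has not worsened does not count as an SAE". Both sections also have a separate exemption: "In the absence of an AE, the investigator should not report hospitalization or prolongation of hospitalization". They illustrate it with protocol-required procedures, the centre's own routine, and a third situation, "Hospitalization for survey visits or annual physicals".
- **Section 11.3.9.3** (what the investigator must provide) has its own list, introduced by "While most hospitalizations necessitate reporting of an SAE, some hospitalizations do not require SAE reporting, as follows". The first entry is "Elective or previously scheduled surgery (e.g., a previously scheduled ventral hernia repair". The second is "Procedures for pre-existing conditions that have not worsened after initiation of treatment". Two more cover pre-specified study admissions and hospital visits of under 24 hours without admission. The list closes with one limit: "SAEs must, however, be reported for any surgical or procedural complication resulting in prolongation of the hospitalization".

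The SAP (section 3.9.1 and Table 4) tabulates serious TEAEs and treatment-related SAEs. It has no rule of its own on elective or planned admissions.

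**The concern.** The first exemption in 11.3.9.3 sets no limit on when the operation was arranged, on whether the condition is old or new, or on whether it has worsened. A site that follows this bullet and a site that follows 11.3.1 can therefore classify the same operation differently.

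Three things depend on that choice: the serious flag on the AE record, the SAE form with its 24-hour report, and the event's place in the SAE and related-SAE tables. Section 11.3.9.4 has the sponsor judge expedited reporting on the SAEs it receives, so an event not sent in as an SAE does not enter that review by this route. Safety and tolerability is a stated secondary objective (Protocol 5.2), and the cohorts are small.

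**Working it through.** No figure in the plan bears on this, so the check compares the texts.

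**Step 1. Conditions attached to each exemption for planned admissions**

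| Text | Arranged before the study | Condition already present | Condition not worsened |
|---|---|---|---|
| 11.3.1 | required | required | required |
| 11.3.8 | required | required | required |
| 11.3.9.3, first bullet | not stated | not stated | not stated |
| 11.3.9.3, second bullet | not stated | required | required |

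In the first bullet, *or* makes elective surgery exempt in its own right. The hernia example illustrates only the scheduled kind, and the bullet does not say what the scheduling must precede.

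**Step 2. Does the no-AE exemption close the gap?** It does not. Section 11.2 counts worsening of an existing condition associated in time with study drug as an AE, and also other medical events whatever their cause. A new or worsened condition is therefore an AE. Inpatient admission is a seriousness criterion in 11.3.1.

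**Step 3. Apply both sets of rules to the possible cases**

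| Case | 11.3.1 and 11.3.8 | 11.3.9.3 | Result |
|---|---|---|---|
| Operation arranged before the study, existing condition, not worsened | not an SAE | exempt | agree |
| Elective admission with no AE behind it | not reported | exempt | agree |
| Elective inpatient operation arranged on study for a new condition | SAE | exempt, first bullet | **conflict** |
| Elective or previously scheduled inpatient operation for an existing condition that has worsened | SAE | exempt by the first bullet, though outside the second | **conflict** |
| Urgent admission for a new or worsened condition | SAE | reportable | agree |

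**Step 4. Does anything else in 11.3.9.3 restore these cases?** The closing limit brings back only complications that lengthen the stay. An uncomplicated operation in either conflict row stays exempt.

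**Step 5. The second bullet.** It does not require that the procedure was arranged before the study. Correcting the first bullet alone would leave the lists unmatched.

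**Step 6. Weight of one event.** With 22 subjects per cohort (Protocol Table 5-1) and four KD025 cohorts (4 × 22 = 88), one subject moved into or out of the SAE count changes a cohort's SAE percentage by 1/22 = 4.5 points and the pooled KD025 percentage by 1/88 = 1.1 points. This holds for any single event and does not estimate how many there are.

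**The case against.** The best defence is that the bullet is loosely drafted and was meant narrowly. Its example is a previously scheduled repair, the next bullet is confined to unworsened conditions, and a site that reads the list together with 11.3.1 and 11.3.8 could well reach the intended answer. Section 11.3.9.3 concerns the information to supply; the definition is in 11.3.1 and the duty to report in 11.3.9.2. Several safeguards also remain:

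- Surgery and worsening conditions are named as AEs in 11.2 and must be recorded.
- Under 11.3.9.2 an unexpected, severe AE goes to the sponsor within 24 hours whether or not it is called serious.
- Under 7.2.15 an AE that leads to permanent discontinuation from the study must be promptly reported.
- The event may be serious on another criterion, such as an important medical event.

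Most of this stands and limits the consequence. It does not remove the conflict. If the first bullet covered only unworsened existing conditions, it would largely duplicate the second. A narrow intent is plausible, but it is not written down, and sites work from the wording.

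A reader might also infer that 11.3.1 and 11.3.8 exempt nothing but pre-planned admissions. They do not: both also exempt admissions without an AE. Much elective surgery involves no new or worsened condition and is treated alike everywhere.

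**Conclusion.** The inconsistency is real and confined to elective or previously scheduled inpatient surgery for a new or worsened condition. For that group, the serious classification, the SAE report and inclusion in the SAE tables depend on which section the site applies. This rests on a literal reading of the first bullet.

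Stronger conclusions are tempting, but the documents do not support them:

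- A reader might infer that admissions for new or worsened conditions in general can be left out. Urgent ones are reportable under every section.
- A reader might infer that the events vanish from the safety data or never reach the sponsor promptly. They remain in the AE data, and some must still be sent within 24 hours.
- A reader might put a rate on the omission. The documents give none, so the number of affected events cannot be estimated and may be zero.

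This is a minor to moderate consistency problem in safety reporting. It does not touch the efficacy analyses, the significance level or the sample size.

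**What to change.** Replace the first two exemption bullets of 11.3.9.3 with the rule already in 11.3.1 and 11.3.8: the three-part condition for pre-planned admissions, plus the existing exemption for admissions without an AE. Remove the unqualified word *elective*. This adds no new rule and makes the three sections agree.

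The SAP (section 3.12) says the study was terminated early with 110 subjects, so a wording change alone may come too late for events already recorded. Before database lock, review recorded AEs that involved elective or scheduled inpatient surgery, and classify each against 11.3.1.

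The cost is a short protocol edit, a brief data review and possibly a few more SAE forms.

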#### **11.3.9.4 Regulatory Reporting**

Kadmon Drug Safety (or designee) will process and evaluate all SAEs as soon as the reports are received. For each SAE received, Kadmon will make a determination as to whether the criteria for expedited reporting have been met.

Kadmon (or designee) will submit SAEs that meet the criteria for expedited reporting to the Regulatory Authorities in accordance with local regulations governing safety reporting. Reporting of SAEs by the investigator to his or her IRB will be done in accordance with the standard operating procedures and policies of the IRB. Adequate documentation must be maintained showing that the IRB was properly notified.

As a general rule, treatment codes will be broken by authorized member of the sponsor and/or designee Drug Safety staff before reporting an SAE that meets the criteria for expediting

reporting to the Regulatory Authorities. The investigator and sponsor staff that are not part of the Drug Safety Department will remain blinded to the treatment assignment.

The blind should ordinarily be broken for IND safety reports submitted to the FDA. If a sponsor has concerns that unblinding of AEs will compromise the integrity of the study, the sponsor can propose in advance an alternative reporting format or frequency to maintain the blind that must be agreed to by the director of the review division in FDA with responsibility for review of the IND (21 CFR 312.32(c)(3)). Other Safety Considerations

#### **11.3.10 Laboratory Data**

All laboratory data obtained during the course of the study should be reviewed. Any abnormal value that leads to a change in subject management (e.g., dose delay, requirement for additional medication or monitoring) or is considered to be of clinical significance by the investigator should be reported as an AE and/or SAE as appropriate, unless this value is consistent with the subject's present disease state or is consistent with values obtained prior to entry into the study.

With the exception of LFTs, laboratory results will be classified using the Toxicity Grading Scale for Healthy Adult and Adolescent Volunteers Enrolled in Preventive Vaccine Clinical Studies (see Appendix A). LFTs will be classified using Table 9-2 in Section 9.4.

#### **11.3.11 Medication Errors**

Any medication error that results in an AE, even if it does not meet the definition of serious, requires reporting within 24 hours to the safety monitor.

#### **11.3.12 Follow-Up of Adverse Events**

Any SAE or AE assessed as possibly related that led to treatment discontinuation (including clinically significant abnormal laboratory values that meet these criteria) and is ongoing 30 days after last dose of study treatment must be followed until either resolution of the event or determination by the investigator that the event has become stable or irreversible. This follow-up guidance also applies to possibly related SAEs that occur more than 30 days after last dose of study treatment. The status of all other continuing AEs will be documented as of 30 days after last dose of study treatment.

## 12 STATISTICAL CONSIDERATIONS

All descriptive and inferential statistical analyses will be performed using SAS statistical software (Version 9.4), unless otherwise noted. For categorical variables, the number and percent of each category within a parameter will be calculated for non-missing data. For continuous variables, the mean, median, and standard deviation (SD), as well as the minimum and maximum values, will be presented.

Statistical significance will be declared when the p-value is found to be  $\leq 0.05$ , unless otherwise noted. Missing data will not be imputed unless otherwise stated. All clinical data captured will be provided in data listings.

Complete details of the planned analysis will be documented in the SAP.

### 12.1 General Design

All data for enrolled subjects will be presented in data listings by subject number. For those summary tables in which baseline and change from baseline measurements will be presented, the last observed measurement prior to the initial dose of KD025 will be considered the baseline measurement.

Continuous data will be described using descriptive statistics: number of observations (n), mean, SD, median, minimum, and maximum. Frequencies and percentages will be used for summarizing discrete (categorical) data. When categorical data are presented, the percent will be suppressed when the count is zero in order to draw attention to the non-zero counts. The denominator for all percentages, unless otherwise specified, will be the number of subjects in the specified analysis population. Two-sided 95% confidence interval employing the exact binomial method will be provided for efficacy activity endpoints.

Hypothesis testing, if appropriate, will be carried out at the 5% (2-sided) significance level. Due to the exploratory nature of the study, no adjustments may be made for the multiplicity of endpoints. Non-parametric tests may be used in preference to parametric tests if the underlying distributions of the data are not known. Missing values will not be imputed. If a subject does not have sufficient data for a particular analysis, then, that subject will be excluded from that

analysis. Endpoints defined as an average of multiple measurements will be used for those data points that were non-missing, and the denominator will be adjusted accordingly.

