### **12.3 Study Populations**

Two populations will be employed in the analysis of study data:

- The modified intent-to-treat (mITT) population will consist of all subjects who are randomized and take at least 1 dose of study drug. All safety analyses will be performed on the mITT population. The Evaluable for Efficacy population will consist of subjects who have non-missing baseline and Week 16 PASI scores and do not have a major protocol violation.

Demographics, subject disposition, and screening and baseline characteristics will be summarized for mITT populations, where appropriate.

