3.8 Efficacy Analysis

3.8.1 Primary Endpoint

- The number (%) of subjects with a 75% decrease in PASI by Week 16
In addition to the descriptive statistics (n, %, CI) for each group, the difference of the percentage of subjects with a 75% decrease in PASI by Week 16 between each treatment and control group will be analyzed with Fisher's exact method.

Patients without Week 16 assessment will be counted as failed to reach 75% decrease.

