3.12 Sample Size Justification

A sample size of 36 subjects per cohort receiving KD025 will provide approximately 90% probability of 1 or more subjects in the cohort experiencing an AE that has an underlying rate of $\geq 6\%$ and approximately an 80% probability of 1 or more subjects in the cohort experiencing an AE that has an underlying rate of $\geq 4\%$.

An evaluable sample size of 30 subjects per cohort will provide approximately 85% power to detect a difference in the number of subjects that reach PASI 75 rates at Week 16 between a KD025 group and placebo, assuming rates of 33% and 5%, respectively, at a 5% 2-sided significance level using Fisher's Exact test. This assumes an observed case analysis with approximately 17% of subjects not having a Week 16 PASI score.

But due to newly available plaque psoriasis treatment, this study was terminated early with 110 subjects.

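### SAP 3.12's 85% power is about 73% under the Fisher test it names, and its observed-case basis and the protocol's exclusion rule both differ from the SAP's missing-as-failure primary analysis

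*Protocol*

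**What the plan says.** **Power.** SAP 3.12 states: "An evaluable sample size of 30 subjects per cohort will provide approximately 85% power". The inputs are "assuming rates of 33% and 5%, respectively", "at a 5% 2-sided significance level", with Fisher's exact test named as the method. It continues: "This assumes an observed case analysis with approximately 17% of subjects not having a Week 16 PASI score". The safety sentence of the same section gives the planned enrolment: "A sample size of 36 subjects per cohort receiving KD025". The section ends by recording that the trial stopped early with 110 subjects. It gives no power for that size, and Protocol 12.2 makes no power claim.

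**Missing data, protocol.** Section 12.1 says "Missing values will not be imputed" and leaves a subject with insufficient data out of the analysis concerned. Section 12.3 adds: "The Evaluable for Efficacy population will consist of subjects who have non-missing baseline and Week 16 PASI scores", and also requires no major protocol violation. The opening of Section 12 is softer: it allows imputation where stated and leaves full details to the SAP.

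**Missing data, SAP.** Section 3.2 puts efficacy on the mITT population and defines no Evaluable for Efficacy set. Section 3.8.1 says: "Patients without Week 16 assessment will be counted as failed to reach 75% decrease". Section 3.1.5 drops missing data from percentages unless another rule is specified. Section 3.1.2 says LOCF will be used where applicable, without naming an endpoint.

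**The concern.** There are two separate problems.

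The first is the power statement. It names a test, a sample size and two rates, so it can be checked. It also describes an observed-case analysis, which is not the analysis that Section 3.8.1 will run. If the trial finds no difference, a reader who relies on 85% will take the result as firmer evidence against an effect than a trial of 110 subjects can give.

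The second is the missing-data rule for the primary endpoint. The protocol's general rule excludes a subject without a Week 16 PASI; the SAP keeps that subject as a non-responder. The denominators differ, so the PASI 75 percentages differ, and in a small trial significance can differ too. The SAP does not acknowledge a departure from the protocol.

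**Working it through.** **Inputs.** From SAP 3.12: 33% v 5%, two-sided 5%, Fisher's exact test, 30 evaluable and 36 planned per cohort, about 17% missing (1 − 30/36 = 16.7%). From SAP 2.2 and 3.12: 110 subjects in five equal cohorts, 110/5 = 22 each.

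**Method.** For two independent binomials with n per arm,

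power = Σ Bin(x; n, p1) · Bin(y; n, p2), summed over all tables (x, y) whose two-sided Fisher p-value is ≤ 0.05.

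**Step 1: reproduce the stated figure** (n = 30 per arm, 33% v 5%).

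| Method | Power |
|---|---|
| Fisher's exact, two-sided 5% (as named) | 73.1% |
| Normal approximation, pooled variance | 80.5% |
| Normal approximation, unpooled variance | 84.1% |
| Chi-square without continuity correction | 84.5% |
| Arcsine | 84.9% |

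Two of these can be checked by hand:
- Unpooled: SE = √[(0.33×0.67 + 0.05×0.95)/30] = 0.0946; 0.28/0.0946 − 1.96 = 1.00; Φ(1.00) = 84.1%.
- Arcsine: h = 2·arcsin√0.33 − 2·arcsin√0.05 = 0.773; 0.773×√15 − 1.96 = 1.03; Φ(1.03) = 84.9%.

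So 85% is what an uncorrected large-sample formula gives at 30 per arm. Fisher's test comes close only at 36 per arm with nobody missing (84.2%).

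**Step 2: apply the SAP 3.8.1 rule.** Assume 17% missing in each arm, independent of response. The rates on all dosed subjects become 0.33×0.83 = 27.4% and 0.05×0.83 = 4.15%.

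| Size per arm | Observed cases | Missing counted as failure (17%) | None missing |
|---|---|---|---|
| 36 planned (30 observed) | 73.1% | 72.1% | 84.2% |
| 22 actual (18 observed, 22×0.83 = 18.3) | 46.4% | 47.2% | 59.5% |

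Reading across the first two power columns, the choice of rule changes power by about one point, down at the planned size and up at the actual size. Reading down, the smaller trial costs about 25 points (72.1% to 47.2%, or 84.2% to 59.5%).

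Other missing rates at 22 per arm under the failure rule: 5% gives 56.1%, 10% gives 52.5%, 20% gives 44.8%.

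**Step 3: effect of the rule on the estimate.** With 17% missing, an observed-case rate of 33.0% is 27.4% under the failure rule, a difference of 5.6 points.

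**Step 4: can the rule decide significance?** A constructed example at 22 per arm: 6 v 1 responders, with 5 active and 2 placebo subjects missing Week 16 (7/44 = 16%).
- Exclude them: 6/17 v 1/20, Fisher p = 0.033.
- Count them as failures: 6/22 v 1/22, Fisher p = 0.095.

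The numbers are hypothetical. They show only that the choice can matter.

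**The case against.** **The power text has been overtaken by events.** SAP 3.12 itself says the trial stopped at 110, and no decision still depends on 85%. This stands as far as it goes: sample size cannot be repaired. But the figure is not marked as superseded, and no other power figure appears in either document.

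**The SAP is entitled to set the rule.** Protocol 12 allows stated exceptions and refers to the SAP for details. Protocol 12.1 sets percentage denominators to the specified analysis population, which suits the SAP rule. Protocol 12.3 never assigns the primary analysis to the Evaluable for Efficacy set. Within the SAP, 3.1.5 admits exceptions and 3.8.1 is one, so those two sections agree. All of this softens the conflict. It does not remove the unqualified exclusion in Protocol 12.1, explain why a protocol-defined efficacy set is dropped, or reconcile SAP 3.12 with SAP 3.8.1.

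**Stronger readings to avoid.**
- A reader might infer that counting missing subjects as failures is what cost the design its 85%. The table in Step 2 shows otherwise: the shortfall is already there for observed cases.
- A reader might infer that dropout will be dose-related because of the liver criteria in Protocol 9.4, so that the choice of rule biases the comparison. Protocol 4.3 reports liver enzyme elevations in about 20% of subjects in an earlier study, highest on a regimen not used here. Neither document gives discontinuation by dose, so this remains conjecture.
- A reader might take 47% as the power of the trial. It depends on the assumed 17%. SAP 2.2 and Protocol 5.6 speak of 22 evaluable per cohort from 110 subjects, which leaves no room for loss and would give 59.5%.

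**Conclusion.** The point holds in two limbs. First, SAP 3.12 is wrong as written: with the test, rates and sample size it names, power is about 73%, not 85%. Its observed-case basis also does not match the primary analysis, though that mismatch is worth only about one point. At the actual size, power under the SAP rule is about 60% with none missing, falling to about 47% with 17% missing. These figures assume true rates of 33% and 5% among observed subjects, 22 per arm, and missingness equal across arms and independent of response. If 33% and 5% were instead rates with missing already counted as failure, 36 per arm would have given 84%; but the SAP says the figure is for observed cases.

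Second, Protocol 12.1 and 12.3 conflict with SAP 3.2 and 3.8.1 on who is in the primary denominator, a difference of 5.6 points in a 33% rate at 17% missing. The SAP rule is clear and sound. What is missing is an acknowledgement that it departs from the protocol, and a statement that the LOCF sentence does not reach this endpoint.

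**What to change.** 1. **SAP 3.12:** correct 85% to about 73% for Fisher's exact test at 30 evaluable per cohort, and mark the paragraph as superseded by the early stop. Add power for the actual size under the 3.8.1 rule: at 22 per arm, about 60% with none missing to about 47% with 17% missing, with the assumptions stated.
2. **SAP 3.2 and 3.8.1** (and Protocol 12.1 and 12.3 if the protocol is amended): state that the primary analysis is mITT with a missing Week 16 PASI as non-response, and that this departs from Protocol 12.1 and 12.3.
3. **SAP 3.1.2:** state that LOCF does not apply to the primary endpoint.
4. **Sensitivity analysis:** report PASI 75 in the protocol's Evaluable for Efficacy set. This set is narrower than observed cases, because it also removes major protocol violators.

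SAP 3.1.5 needs no change. The cost is some wording, one extra table and a less favourable stated power. No new data are needed.
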